- Abnormal EKG consistent with coronary artery disease or increased risk of malignant arrhythmia including, but not limited to, evidence of active ischemia, prior myocardial infarction, proximal LAD critical stenosis (Wellen's sign), prolonged QT interval (> 440 ms). Non-specific ST segment and T wave

changes are not grounds for exclusion in the absence of symptoms or history of heart disease. A reassuring evaluation by a cardiologist after an abnormal EKG finding may allow participation.

- History of hypoglycemic seizures (grand mal) or coma in the last year
- History of poor venous access or inadequate venous access as determined by trial nurse or physician at time of screening
- Hemoglobin < 12 g/dl for men, < 11 g/dl for women
- Any factors that, in the opinion of the principal investigator would interfere with the safe completion of the study

III. c. Source of Subjects

Volunteers who fit the selection criteria will be considered as candidates for this study. We will contact individuals who have previously inquired about participation in our studies and have asked us to have their contact information kept on file. In addition, advertisements for the study may be posted at the MGH Diabetes Center and other places, and may be distributed in the weekly broadcast email of research studies seeking volunteers. A letter may be sent to adult endocrinologists in the Boston metropolitan as well as selected nearby endocrinologists informing them of the study and asking them to refer any eligible patients who might be interested. We will post information about the trial along with contact information on our website www.bionicpancreas.org and on www.clinicaltrials.gov.

IV. Subject Enrollment

IV. a. Number of Subjects

It is expected that we will have 12 subjects complete the study and reach a plasma glucose of <60 mg/dl for 3 measurements at 5 minute intervals or a plasma glucose of <50 mg/dl for 1 measurement. We expect that the experiments and analysis can be accomplished over a period of 6-12 months. Up to 24 subjects will be enrolled. The upper bound is based on the expectation that some volunteers will be excluded after the screening visit, the possibility that some experiments may have to be discontinued before completion, and the likelihood that some subjects will not reach the hypoglycemic threshold during the experiment.

IV. b. Enrollment and Consent Procedures

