- A urine pregnancy test will be performed in female volunteers upon arrival to the study visit. If the test is positive the volunteer will be informed of the result and the visit will be ended. The date of the last menstrual period will also be documented, along with usual cycle length, for female subjects.
- A plasma glucose will be checked via fingerstick using the Contour Next One meter upon arrival. If PG is ≥250 mg/dL the visit will be rescheduled. If PG is <50 mg/dL, the patient will be treated with simple carbohydrates according to the 15/15 rule (15 grams of ≥carbohydrates, repeated in 15 minutes if necessary). If PG is <70 mg/dL and the patient has symptoms of hypoglycemia they may elect to be treated with simple carbohydrates according to the 15/15 rule (15 grams of ≥carbohydrates, repeated in 15 minutes if necessary).
- We will ask subjects to avoid certain skin care products that will interfere with sweat sample collection on the day of the visit.
- We will ask subjects to bring a breakfast of their choosing to the visit.
- A 20 gauge or smaller peripheral I.V. will be placed.
- Subjects will calculate their insulin dose based on their insulin to carbohydrate ratio for the breakfast meal they brought to the visit. A correction bolus of insulin will also be added to the meal correction dose.
 - The dose of insulin will be calculated using their own correction factor, correcting them down to a target PG of 40 mg/dl using their current PG.
 - O Both doses of insulin will be combined into one syringe and injected into the subcutaneous tissue.
- Subjects will then eat breakfast.
- BG measurements using the YSI will be obtained per the following protocol:
 - o If PG is ≥ 120 mg/dl, BG measurements will be obtained off the IV line every 30 minutes.
 - o If PG is 100-119 mg/dl, BG measurements will be obtained off the IV line every 20 minutes.
 - o If PG is 80-99 mg/dl, BG measurements will be obtained off the IV line every 10 minutes.
 - o If PG is < 80 mg/dl, BG measurements will be obtained off the IV line every 5 minutes.
 - Study staff will collect samples of sweat from the subject's underarm and will ask subjects to exhale into a breath collection device throughout the visit, with increased frequency during any episodes of hypoglycemia. These samples will be collected, de-identified and shipped out to collaborators at the MITRE Corporation for analysis of the relationship between volatile organic compounds in breath and sweat and hypoglycemia.

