- Subjects will be required to treat with 15g of rapid acting carbohydrates:
 - If PG <50 mg/dl for two consecutive measurements
 - o If PG is <40 mg/dl for one measurement
- Subjects will be given the option to treat with 15g of rapid acting carbohydrates:
 - O If PG is <60 for three consecutive measurements
 - If PG is <50 mg/dl for one measurement
 - O Repeat treatments will be given at 15 minute intervals if hypoglycemia continues
 - If the YSI fails, the Contour Next One meter will be used for glucose measurements.
- If the subject reaches a hypoglycemia threshold they will be treated with carbohydrates as above and
 they will be discharged from the DRC when they have maintained a PG ≥ 70 mg/dl for 1 hour. They will
 be allowed to treat with further oral carbohydrates at their discretion during this time to maintain their
 blood glucose.

- If the subject does not reach the hypoglycemia threshold 3 hours after the insulin injection, another correction bolus will be given via syringe per the same protocol:
 - The dose of insulin will be calculated using their own correction factor, correcting them down to a target PG of 40 mg/dl using their current PG.
 - o If the subject does not reach the hypoglycemia threshold after an additional two hours, they will be permitted to eat breakfast and be discharged.
- If the subject reaches a hypoglycemia threshold a hypoglycemia threshold they will be treated with carbohydrates as above and they will be discharged from the DRC when they have maintained a PG ≥ 70 mg/dl for 1 hour. They will be allowed to treat with further oral carbohydrates at their discretion during this time to maintain their blood glucose.

VI. Bio Statistical Analysis

VI. a. Data Collected

VI. a. 1. Prior to start of experiment:

- Age
- Sex
- Race and ethnicity
- Date of last menstrual period in female subjects
- Date of diabetes diagnosis
- Medical, surgical, and social history, allergies, and review of systems relevant to inclusion and exclusion criteria
- Medications (prescription and non-prescription) and date of last change in medication regimen
- Insulin regimen
- Average total daily dose of insulin in the last 30 days as available
- Height and weight
- Blood pressure
- EKG if applicable
- Hemoglobin A1c
- Hemoglobin
- Urine HCG (pre-menopausal females)

VI. a. 2. During the experiment:

- Plasma glucose
- Breath and sweat VOCs
- Carbohydrate intake

VI. b. Study Endpoints

VI. b. 1. Primary endpoint analyses

VOC outcomes

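### A subject who does not reach the hypoglycemia threshold may go home two hours after a second insulin bolus with no minimum plasma glucose at exit

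*Combined protocol and SAP*

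**What the plan says.** Section V.d.ii (Visit Procedures) sets two exit routes.

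- **Subjects who reach the threshold** are treated with carbohydrates, and "they will be discharged from the DRC when they have maintained a PG ≥ 70 mg/dl for 1 hour". During that hour, "They will be allowed to treat with further oral carbohydrates at their discretion during this time to maintain their blood glucose". The rule appears twice, and each time it is limited to subjects who reach a threshold.
- **Subjects who do not reach it** are dosed again: "If the subject does not reach the hypoglycemia threshold 3 hours after the insulin injection, another correction bolus will be given via syringe". The dose is worked out from the subject's own correction factor, "correcting them down to a target PG of 40 mg/dl using their current PG". Two hours later: "If the subject does not reach the hypoglycemia threshold after an additional two hours, they will be permitted to eat breakfast and be discharged".

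Section IV.a describes the threshold as subjects who "reach a plasma glucose of <60 mg/dl for 3 measurements at 5 minute intervals or a plasma glucose of <50 mg/dl for 1 measurement". The triggers for optional carbohydrate treatment in section V.d.ii use the same cut-offs. Section IV.a also expects the second route to be used, since it justifies the enrollment ceiling partly by "the likelihood that some subjects will not reach the hypoglycemic threshold during the experiment".

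No other section gives a glucose criterion for discharge or a contact after discharge.

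**The concern.** The protocol treats a PG below 70 mg/dl as too low to send home a subject who has just been hypoglycemic. It sets no such floor for a subject who has had two insulin doses, the second only two hours before permitted exit. As written, the second dose depends on current PG and the correction factor, with no stated reduction for the first injection.

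Section VII rests its low estimate of risk on close glucose monitoring, treatment rules and constant clinical supervision. All of these stop when the subject leaves. Noticing a later fall unaided cannot be taken for granted: impaired awareness of hypoglycemia is assessed at screening (section V.a) but is not a listed exclusion (section III.b). What is at stake is the safety of these subjects in the hours after the visit.

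**Working it through.** The plan gives no figure to reproduce, so the check sets the two rules side by side and follows the clock.

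**Inputs.** Threshold: section IV.a. Dosing, sampling and discharge rules: section V.d.ii. Section V.d.ii does not define the threshold itself, so the section IV.a definition is used. If the stricter mandatory-treatment triggers were meant (below 50 mg/dl twice, or below 40 once), more subjects would count as not reaching it and the gap would be wider.

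**Timeline for a subject who does not reach the threshold.** First injection at 0 h; second bolus at 3 h; discharge permitted at 3 + 2 = 5 h, which is 2 h after the last dose.

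**Which glucose values are compatible with that exit?**

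| Readings up to the two-hour mark | Threshold met? | Minimum PG required to leave |
|---|---|---|
| One reading below 50 | Yes | At least 70 for 1 hour |
| 59, 59, 59 | Yes | At least 70 for 1 hour |
| One or two readings of 50-59 only | No | None stated |
| 60, 60, 60, or any values of 60-69 | No | None stated |

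So values of 60-69 mg/dl, and one or two values of 50-59, do not bar discharge on the second route. All of them would bar it on the first.

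**Is the glucose known at that point?** Yes. The sampling schedule is not switched off after the second bolus: "If PG is < 80 mg/dl, BG measurements will be obtained off the IV line every 5 minutes". A subject who stayed in one band for the whole two hours would contribute:

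- below 80 mg/dl: 120/5 = 24 intervals
- 80-99: 120/10 = 12
- 100-119: 120/20 = 6
- 120 or above: 120/30 = 4

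In the range that matters, the latest value is at most about 5 minutes old. The information exists; the exit rule sets no floor on it.

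**Does the meal close the gap?** Not as written. It is permitted rather than required, and neither a carbohydrate amount nor a PG check after it is specified.

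**The case against.** The strongest case on the other side has four parts.

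*The two rules address different states.* The 1-hour hold checks recovery after actual hypoglycemia and treatment. The other group has stayed out of the threshold through two doses and 5 hours of sampling, is offered food, and is supervised by clinicians experienced in hypoglycemia. The wording allows discharge and does not compel it, and recent hypoglycemic seizure or coma is an exclusion. All this stands and makes the point modest. It does not supply a floor: staff following the text may release a subject at 60-69 mg/dl.

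*Glucose does enter the rule.* A reader might infer that no glucose value governs discharge of this group, or that they go unmonitored. Neither is supported. Not reaching the threshold is itself defined by PG, and sampling continues. What is missing is a minimum at exit.

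*Subjects who reach the threshold are not always kept longer.* A reader might infer this from the 1-hour hold. Suppose, for illustration, that a subject crosses 30 minutes after the second bolus, recovers in 15 minutes and then holds for 60: 30 + 15 + 60 = 105 minutes, or 1 h 45 min after that bolus. This is sooner than the 2 hours that apply to anyone on the second route. The difference lies in the exit condition, not in a general difference in length of stay. The 59 versus 60 contrast is likewise an edge case of the kind any cut-off produces; it shows where the rule changes, not how often.

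*Harm is not demonstrated.* A reader might infer that subjects will become hypoglycemic after leaving. The documents give no duration of action for the insulin and no expected glucose distribution at the two-hour mark. Section IV.a expects some subjects to miss the threshold, but does not say that any will be at 60-69 mg/dl when they leave.

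**Conclusion.** The point holds as a modest participant-safety improvement that is cheap to make. The second exit route has no minimum PG, so it permits discharge at 60-69 mg/dl, or after one or two readings of 50-59, two hours after a dose aimed at 40 mg/dl. The same protocol does not accept such values for discharge by the other route.

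The textual gap is certain, given the section IV.a threshold. Its practical size is not: neither the number of subjects affected nor any later fall can be derived from the documents. Nothing here touches the endpoints, the VOC comparison or the number of subjects who complete.

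**What to change.** Replace the discharge sentence for subjects who do not reach the threshold with a rule to this effect:

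> Two hours after the second bolus, a subject still short of the hypoglycemia threshold is given a meal or snack and may leave if PG is ≥70 mg/dl and not falling on the last two measurements. Otherwise the subject is treated with carbohydrates, sampling continues on the same schedule, and discharge follows once PG has stayed ≥70 mg/dl for 1 hour.

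The trend condition matters because a single value just above 70 mg/dl may be a point on a decline. A meal or snack is also the better term, since section V.d.ii has subjects eat breakfast after the first injection.

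**Cost.** A short change of wording. Subjects at or above 70 mg/dl and not falling leave when they do now. The others stay longer, with added draws per hour of 60/5 = 12 below 80 mg/dl, 60/10 = 6 at 80-99, 60/20 = 3 at 100-119 and 60/30 = 2 at 120 or above. Volume per draw is not stated. At an assumed 1-3 ml, an hour at 70-79 mg/dl adds 12-36 ml, against the typical limit of 170 ml in section VII (36/170 = 21% at most). Read literally, the trend condition also catches a subject drifting down from a high value; the sponsor could limit it to a stated PG range.

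Holding every such subject for a further hour is not needed: it would also detain those well above 100 mg/dl and would be stricter than the rule it is meant to match.
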